8. SECONDARY STATISTICAL ANALYSES

8.1. Efficacy Analyses

8.1.1. Overview of Planned Efficacy Analyses

The secondary efficacy analyses will be based on the IPP population, unless otherwise specified. Table 5 provides an overview of the planned efficacy analyses, with full details of data displays being presented in Appendix 13: List of Data Displays. Given the small number of subjects, only time to respiratory response will be summarized. Data relevant to other secondary endpoints will be listed including vital signs, ventilation status, hospital discharge, hospital re-admission, and ICU stay.

Table 5 Overview of Planned Secondary Efficacy Analyses

Endpoint	Stats Analysis			Analysis Summary		ummary Individua	
	Т	F	L	T	F	F	L
	Absolute						
Time to Respiratory Response (TTRR)				Y [1]			

^[1] Proportion of clinical response and Kaplan Meier estimates for the median of TTCR for each treatment group and the median difference and 95% CI between two comparisons: each DNX arm and OSV will be provided

8.2. Safety Analyses

8.2.1. Overview of Planned Adverse Events Analyses

The safety analyses will be based on the Safety population, unless otherwise specified. The summaries include on-treatment and post-treatment assessments unless otherwise noted.

Table 6 provides an overview of the planned analyses, with further details of data displays being presented in Appendix 13: List of Data Displays.

Table 6 Overview of Planned Adverse Event Analyses

Endpoint / Parameter/ Display Type		Absol	ute
	Sun	nmary	Individual
	Т	F	L
Adverse Events (AEs)			
All AEs by SOC and Maximum Grade	Υ		Υ
All AEs by Overall Frequency	Υ		
Grade 2-4 AEs by Overall Frequency	Υ		
All Drug-Related AEs by Overall Frequency	Υ		
All Non-Serious AEs by Overall Frequency	Υ		
Drug-Related Grade 2-4 AEs by Overall Frequency	Υ		
Relationship Between AE SOCs, PT & Verbatim Text			Y
Listing of Adverse Events for Subjects with Neutropenia by Grade (>=Grade 1)	Y [1]		
Serious and Other Significant AEs			
Fatal Serious AEs			Y
Non-Fatal Serious AEs	Υ		Υ
Serious AEs by SOC	Υ		
Reasons for Considering as a Serious AE			Y
Drug-Related Non-Fatal Serious AEs	Υ		
Drug-Related Serious AEs by SOC	Υ		
Adverse Events Leading to Withdrawal from Study by Overall Frequency			Υ
Adverse Events Leading to Permanent Discontinuation of Study Treatment by			Υ
Overall Frequency			1
Summary of Serious Adverse Events by System Organ Class and Preferred	Υ		

Endpoint / Parameter/ Display Type	Absolute		ute
	Sun	nmary	Individual
	Т	F	L
Term (Number of Subjects and Occurrences)			
Summary of Non-serious Adverse Events by System Organ Class and Preferred Term (Number of Subjects and Occurrences)	Y		

NOTES:

- T = Table, F = Figures, L = Listings, Y = Yes display generated, SOC = System Organ Class, PT = Preferred Term
- Summary = Represents TF related to any summaries (i.e. descriptive statistics) of the observed raw data.
- Individual = Represents FL related to any displays of individual subject observed raw data.
- [1]. Toxicity Grading is based on the Division of AIDS Grading (Section 12.5 of the protocol)

8.2.2. Overview of Planned Clinical Laboratory Analyses

The safety analyses will be based on the Safety population, unless otherwise specified. The summaries include on-treatment and post-treatment assessments unless otherwise noted.

Table 7 provides an overview of the planned analyses, with further details of data displays being presented in Appendix 13: List of Data Displays.

Table 7 Overview of Planned Clinical Laboratory Analyses

Endpoint / Parameter/ Display Type		Absolute			ange	from BL	
	Sum	Summary Individ		Sumr	nary	Individual	
	Т	F	L	Т	F	L	
Chemistry							
Summary of Data Supporting Safety Halting Criteria	Y [1]						
Chemistry Changes from Baseline				Υ			
Creatinine by Visit	Υ	Υ		Υ			
Hematology Changes from Baseline				Υ			
Individual Plot of Absolute Neutrophils Count by Visit by Subject		Υ					
All Laboratory	_						
Summary of Maximum Treatment Emergent Toxicities of All Lab Parameters	Υ						
Laboratory Data Abnormalities of Potential Clinical Importance (Grade 3-4)						Y	

NOTES:

- T = Table, F = Figures, L = Listings, Y = Yes display generated, PCI = Potential Clinical Importance
- Summary = Represents TFL related to any summaries (i.e. descriptive statistics) of the observed raw data.
- Individual = Represents FL related to any displays of individual subject observed raw data
- [1] Summary includes the proportion of subjects with creatinine increase of 0.5 mg/dl on 2 consecutive visits

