4.1.1. Sentinel Cohorts with Enhanced Safety Monitoring

Sentinel cohorts with enhanced safety monitoring will be enrolled as part of a step-wise enrollment of subjects with different levels of renal impairment and disease severity (less severe and critically ill, Section 4.3). Subjects in the sentinel cohorts will have more stringent eligibility criteria (baseline creatinine clearance criteria and exclusion of subjects with diabetes mellitus and chronic kidney disease). The IV DNX formulation developed for this study contains 750 mg β -Cyclodextrin Sulfobutylether (SBE- β -CD, Captisol) per 50 mg of GSK1325756 (free base equivalent [FBE]), to achieve the desired

[figure not shown]
5mg/mL concentration (FBE) and ensure DNX remains in solution when added to the IV saline bag. Captisol is renally cleared with the potential for accumulation in subjects with severe renal impairment. As such, this study includes enhanced monitoring to evaluate for renal function. Subjects in the sentinel cohorts will undergo serum creatinine, eGFR and urine output assessments twice a day for the treatment period. Additional enhanced monitoring will be based on disease severity, peripheral neutropenia and bacterial infections.

Approximately 30 subjects who are less severely ill and have baseline creatinine clearance within normal reference ranges (creatinine clearance ≥ 80 mL/min) will be enrolled in sentinel cohort 1 (Figure 1). The IDMC will first review available safety data after completion of the PT Day 3 visit, from approximately 10 subjects who are less severely ill and have normal renal function enrolled in sentinel cohort 1. Enrollment of subjects with normal renal function will continue during this review.

Following a review of all available data from the approximately 30 subjects in sentinel cohort 1, and an acceptable outcome from the IDMC, approximately 10 subjects with mild renal impairment, defined as baseline creatinine clearance of 50-79 mL/min will be enrolled in sentinel cohort 2, while continuing to enroll subjects with normal renal function in the study. At this stage, both less severely ill and the more critically ill subjects may be enrolled.

The IDMC will review the available safety data after completion of PT Day 3 from subjects in sentinel cohort 2 with mild renal impairment. Additional subjects with mild renal impairment will not be enrolled until the safety review is conducted by the IDMC, and the determination of an acceptable outcome.

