5.4.4. Other Stopping Criteria

Subjects should be permanently discontinued from IP if any of the following conditions are met:

- Serum creatinine: 0.5 mg/dL increase from baseline, on 2 successive readings;
- eGFR of <60 on two consecutive readings using the CKD-EPI calculation (eGFR of <30 for moderate renal impairment);
- Peripheral neutropenia: absolute neutrophil counts <0.5 Gi/L on 2 successive assessments.

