- o. Serum creatinine level required at Baseline and twice daily during treatment for subjects in the sentinel cohort. For all other subjects, serum creatinine level required at Baseline and once daily during treatment (local testing (L) for subject management as well as central testing(C)).
- p. Hematology panel including CBC with differential required every other day during treatment (local testing (L) for subject management as well as central testing(C))
- q. Urine output to be measured twice daily for subjects in the sentinel cohort.
- r. Ultrasensitive urine or blood pregnancy test required in women of childbearing potential prior to dosing and 3 days post last dose of study treatment.
- s. Nasopharyngeal swab will be used for influenza Subtype RT-PCR, qRT-PCR, quantitative culture and may also be used for rapid influenza diagnosis; Will also be used for viral genotyping and phenotyping if needed and multiplex PCR assay.
- t. Nasal swab collected for influenza diagnostic test or other local test for influenza diagnosis

- u. BAL samples (for biomarkers) are requested only if the procedure/sampling is being carried out for routine management of the patient and at any timepoint throughout the study
- v. Endotracheal aspirates (biomarkers/neutrophil counts) are required for subjects who are intubated.
- w. Nasal samples for biomarkers will be collected at the days indicated from all subjects using nasal SAM strips.
- x. An optional procedure, nasal wash, will be used to collect nasal samples from as many non-intubated subjects as feasible.
- y. PK samples will be drawn on Day 1 (pre-dose), Days 3 and 5 to coincide with PD measurements (nasal washes if done, endotracheal samples and a blood draw for exploratory biomarkers). In sentinel cohort 1 (less severe subjects with normal renal function), PK samples will be additionally drawn on Day 3 at pre-dose, and 0.5, 1 (end of infusion), 1.5, 2, 3, 4, 8 and 12 hours post-dose. **Note: PK draws must be collected from the opposite arm from the infusion arm.**
- z. Informed consent for optional substudies (e.g., genetic research and transcriptomics), must be obtained before collecting samples. In subjects who consent, a blood sample for genetic research is collected at the baseline visit, or at the earliest point possible during the treatment period for genetic research testing; blood samples for transcriptomics are taken on each of the indicated days and used to evaluate changes in transcriptome profiles.

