11.5.3. Reporting Process & Standards

Reporting Process			
Software	Software		
The currently support to the currently su	The currently supported versions of SAS and TSCG software will be used.		
Reporting Area			
HARP Server	: US1SALX00259		
HARP Area	: \ARPROD\GSK1325756\MID201023\Final_xx		
QC Spreadsheet : \ARWORK\GSK1325756\MID201023\Final_xx\documents			
Analysis Datasets			

Reporting Process

- Final analysis and IDMC datasets will be created based on Integrated Data Standards Library (IDSL).
- RTF files will be generated for final analysis.

Reporting Standards

General

- The current GSK Integrated Data Standards Library (IDSL) will be applied for reporting, unless otherwise stated:
 - 4.03 to 4.23: General Principles
 - 5.01 to 5.08: Principles Related to Data Listings
 - o 6.01 to 6.11: Principles Related to Summary Tables
 - 7.01 to 7.13: Principles Related to Graphics

Formats

- GSK IDSL Statistical Principles (5.03 & 6.06.3) for decimal places (DP's) will be adopted for reporting of data based on the raw data collected.
- Numeric data will be reported at the precision collected on the eCRF.
- The reported precision from non eCRF sources will follow the IDSL statistical principles but may be adjusted to a clinically interpretable number of DP's.

Planned and Actual Time

- Reporting for tables, figures and formal statistical analyses :
 - Planned time relative to dosing will be used in figures, summaries, statistical analyses and calculation of any derived parameters, unless otherwise stated.
- Reporting for Data Listings:
 - Planned and actual time relative to study drug dosing will be shown in listings (Refer to IDSL Statistical Principle 5.05.1).
 - Unscheduled or unplanned readings will be presented within the subject's listings.
 - Visits outside the protocol defined time-windows (i.e. recorded as protocol deviations) will be included in listings but omitted from figures, summaries and statistical analyses.

Unscheduled Visits

- Unscheduled visits will not be included in summary tables or figures, unless otherwise stated.
 - Unscheduled visits will be included in the maximum toxicity or maximum change from baseline for toxicity tables.
- All unscheduled visits will be included in listings.

Descriptive Summary Statistics		
Continuous Data	Refer to IDSL Statistical Principle 6.06.1	
Categorical Data	N, n, frequency, %	
Reporting of Pharmacokinetic Concentration Data		
Descriptive	Refer to IDSL Statistical Principle 6.06.1	

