11.6. Appendix 6: Derived and Transformed Data

11.6.1. General

Multiple Measurements at One Time Point

- Mean of the measurements will be calculated and used in any derivation of summary statistics but if listed, all data will be presented.
- If there are two values within a visit the value closest to the planned/target day for that visit will be used. If values are the same distance from the target then the mean will be taken.
- Subjects having both High and Low values for Normal Ranges at any post-baseline visits for safety parameters will be counted in both the High and Low categories of "Any visit postbaseline" row of related summary tables. This will also be applicable to relevant Potential Clinical Importance summary tables.

Treatment Start Date

Treatment start date is defined as follows:

 Treatment start date is the date entered onto the IP exposure CRF for when study treatment started.

Study Day

- Calculated as the number of days from initial study treatment start date :
 - Ref Date = Missing → Study Day = Missing
 - Ref Date < Treatment Start Date → Study Day = Ref Date Treatment Start Date
 - Ref Data ≥ Treatment Start Date → Study Day = Ref Date (Treatment Start Date) + 1

Note that Treatment Start Date is considered to be on Study Day 1 and the day before this is Study Day -1; i.e., there is no Study Day 0.

Post-baseline

Post-baseline refers to the combined time periods of On-treatment and Post-treatment.

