11.13.19. Non-ICH Listings

Non-ICH: Listings							
No.	Population	IDSL / TST ID / Example Shell	Title	Programming Notes	Need for early terminated study		
Popula	ition						
29.	ITT-E	POP L1	Listing of Flu Type and Symptoms				
30.	ITT-E	POP L2	Listing of Chest X-Ray Results	Indicate if subject is included	d in IPP		
Efficacy	у						
31.	IPP	EFF L1	Listing of Time to Clinical Response				
32.	IPP	EFF L2	Listing of Time to Respiratory Response				
33.	IPP		Listing of Vital Signs				
34.	IPP		Listing of Ventilation Status – Mechanical Ventilation	Use NAI114373 as a refer Add start and stop time			
35.	IPP		Listing of Ventilation Status – Supplemental Oxygen	Use NAI114373 as a refer Oxygen saturation history should be inc			
36.	IPP		Listing of Hospital Discharge	Include date, duration and r	reason		
37.	IPP		Listing of Subjects Who Were Admitted to Intensive Care Unit				
Safety	Safety						
38.	Safety	LB5	Listing of Absolute Neutrophils for Subjects with Grade 3-4 Absolute Neutrophils or AE of Neutropenia				
39.	Safety	LB5	Listing of Creatinine for Subjects with Creatinine Increase > 0.5 mg/dl in Two Consecutive Visits				

Non-IC	H : Listings				
No.	Population	IDSL / TST ID / Example Shell	Title	Programming Notes	Need for early terminated study
PK					
40.	PK	PK L1	Listing of Whole Blood Danirixin Pharmacokinetic Concentration Data	Include NQ values	
41.	PK	LPK2	Listing of Whole Blood Danirixin Derived Pharmacokinetic Parameters		
Biomar	ker				
42.	ITT-E		Listing of Serum Biomarkers		
43.	ITT-E		Listing of Nasal Wash Biomarkers		
44.	ITT-E		Listing of Nasal SAM Strips Biomarkers		
45.	ITT-E		Listing of BAL Biomarker		
Virolog	У				
46.	ITT-E	VR L1	Listing of Influenza Viral RNA (qRT-PCR and TCID50) in Nasopharyngeal	Use study 201682 as a refe	erence
47.	IPP	VR L2	Listing of Co-infected Subjects		
48.	ITT-E		Listing of Other Viruses by Multiplex RT PCR.		
49.	ITT-E		Listing of Phenotypic IC50 Results	Use NAI114373 as a refer	ence
50.	IPP		Listing of Resistant Mutations in NA and HA Genes	Use NAI114373 as a refer	ence
Health	Outcome			,	
51.	IPP	HO L1	Listing of Hospital Readmission		
52.	IPP	HO L2	Listing of ADL KATZ Score and each ADL Activity		
53.	IPP	HO L3	Listing of 3-Point Scale (Bed Rest, Limit Ambulation, Unrestricted)		

Non-ICH: Listings					
No.	Population	IDSL / TST ID / Example Shell	Title	Programming Notes	Need for early terminated study
54.	IPP	HO L4	Listing of FLU-PRO Total and Domain Scores		

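### The SAP's creatinine flag counts consecutive visits while the protocol's stopping rule counts successive readings, so with twice-daily sentinel sampling the flag can miss subjects who met the rule

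*SAP*

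**What the plan says.** Protocol 5.4.4 lists, among the conditions for permanent discontinuation of investigational product, "Serum creatinine: 0.5 mg/dL increase from baseline, on 2 successive readings". Protocol 4.1.1 sets the sampling frequency: "Subjects in the sentinel cohorts will undergo serum creatinine, eGFR and urine output assessments twice a day for the treatment period". Note o to the Time and Events Table (7.1) agrees: "Serum creatinine level required at Baseline and twice daily during treatment for subjects in the sentinel cohort". Other subjects are sampled once daily. The SAP reproduces this schedule in 11.2.1.

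SAP 8.2.2, Table 7, note [1] has the safety halting summary (display 3.16 in 11.13.7) report, as a proportion, how many subjects had a "creatinine increase of 0.5 mg/dl on 2 consecutive visits". Listing 39 in 11.13.19 is titled "Listing of Creatinine for Subjects with Creatinine Increase > 0.5 mg/dl in Two Consecutive Visits".

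Two general conventions may apply. On repeated values, SAP 11.6.1 says: "If there are two values within a visit the value closest to the planned/target day for that visit will be used", with the mean taken if values are equally close. SAP 11.5.3 says: "Unscheduled visits will not be included in summary tables or figures, unless otherwise stated". The same section keeps unscheduled visits in listings and in the toxicity tables.

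**The concern.** The size of rise and the two-in-a-row structure in note [1] match protocol 5.4.4. Only the unit differs, and the SAP neither explains the difference nor cites another source. With one reading per visit the unit makes no difference. With two readings a day it can.

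Two raised readings on the same day satisfy 5.4.4 but occupy one study-day visit. A confirmatory repeat taken as an unscheduled visit would be left out of the summary table under 11.5.3. In either case the table could show no event for a subject taken off drug under 5.4.4, and so disagree with the discontinuation listing.

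The subject matter gives this some weight. Renal accumulation of the excipient is a named risk in protocol 4.6.1 and the reason for the renal monitoring in 4.1.1. The same risk table makes adding a nephrologist to the IDMC depend on how many subjects are withdrawn under the renal stopping criteria.

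There is also an inconsistency inside the SAP. Note [1] refers to an increase of 0.5 mg/dL with no inequality, as 5.4.4 does, but Listing 39 uses a strict inequality. A subject with rises of exactly 0.5 could be counted in the table and absent from the listing.

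**Working it through.** The plan gives no figure to reproduce, so the two definitions were compared by enumeration.

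**Inputs**
- Reading rule: two adjacent readings both raised (protocol 5.4.4).
- Visit rule: two adjacent visit values both raised (SAP 8.2.2, note [1]).
- Two readings a day for sentinel subjects (protocol 4.1.1; 7.1, note o) over 5 treatment days (protocol 4.2).
- Assumption: a visit is a study day, the column unit of the Time and Events Table.
- For the arithmetic, raised means a rise of 0.5 mg/dL or more. No value or mean used equals 0.5, so the inequality does not affect the results.

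**Adjacent pairs.** Readings: 5 × 2 = 10. Adjacent pairs: 10 − 1 = 9. Pairs within one day: 5. Pairs spanning two days: 9 − 5 = 4. A within-day pair gives one raised visit, so the visit rule cannot fire on it, whichever value represents the day. If treatment runs into Day 6 there are 12 readings and 11 pairs, 6 of them within one day.

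**Dependence on the daily value.** The SAP does not settle how two draws become one visit value, so several conventions were tried. The table gives the number of placements that meet the reading rule but not the visit rule over 5 days.

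| Value used for the day | 2 raised in a row (9 placements) | 3 in a row (8) | 4 in a row (7) |
|---|---|---|---|
| Maximum | 5 | 0 | 0 |
| Mean, rises 0.2 and 0.9 | 5 | 0 | 0 |
| Mean, rises 0.2 and 0.6 | 9 | 8 | 3 |
| First reading | 9 | 4 | 0 |
| Last reading | 9 | 4 | 0 |
| Both must be raised | 9 | 8 | 3 |

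The two mean rows differ because a day with one raised reading averages (0.2 + 0.9)/2 = 0.55 in the first and (0.2 + 0.6)/2 = 0.40 in the second.

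**Worked case under averaging.** Take rises of 0.1 and 0.6 on Day 2, then 0.6 and 0.3 on Day 3. The second and third readings are successive and both 0.6, so the reading rule is met. The daily means are (0.1 + 0.6)/2 = 0.35 and (0.6 + 0.3)/2 = 0.45, so the visit rule is not. This case holds only if the daily values are averaged.

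**Opposite error.** If the first reading represents the day, raised morning values on two days with a normal value between them meet the visit rule but not the reading rule.

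**Once-daily sampling.** With one reading per visit the two rules agreed in every pattern checked.

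**Who is affected.** SAP section 1 reports 10 subjects enrolled. Protocol 5.1 (criterion 8) assigns roughly the first 30 to the normal-renal-function sentinel cohort. Essentially all analysed subjects should therefore be on the twice-daily schedule.

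These are counts of possible placements, not probabilities of a miscount.

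**The case against.** The strongest reply is that two different rules are being compared. Display 3.16 concerns safety halting, and protocol 4.1 places the details of study and arm halting in the IDMC charter. Protocol 5.4.4 is an individual stopping rule. The charter could be visit-based, and the SAP never says that the display applies 5.4.4. This stands as a limit: the matching threshold and structure make a link plausible but do not prove it.

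Second, visit is undefined for morning and evening draws. If each draw is stored as its own visit record, the rules coincide. The averaging convention in SAP 11.6.1 is headed as covering multiple measurements at one time point, so applying it to two planned draws at different times is an inference. This also stands. It makes the omission conditional but leaves the definition missing.

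Third, the exclusion of unscheduled visits does not reach Listing 39, because 11.5.3 keeps them in listings. That is correct, so the exclusion bears only on the summary table.

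Fourth, affected subjects remain visible. Discontinuation reasons are in Table 1.2 and Listing 3, creatinine is plotted by subject in Figure 3.1, and Listing 26 holds all laboratory data. Summaries include post-treatment values, and creatinine continues daily to post-treatment Day 3, so a sustained rise would probably be caught. This limits the harm but does not correct a count that the stated rule can get wrong.

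A reader might go further and infer that the plan would hide renal stopping events, that all 10 subjects would be miscounted, or that renal oversight was compromised. The documents do not support this. Investigators manage subjects on local results (protocol 7.4.6), not on this table. Exposure to the twice-daily schedule is not a likely miscount, and no miscounted subject has been shown.

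**Conclusion.** The point holds in a limited form. The SAP's renal flag uses a different unit from protocol 5.4.4, with no explanation, in a cohort that should be almost entirely on twice-daily sampling. If a visit is a study day, the summary can omit a subject who met 5.4.4. For an episode of exactly two raised readings over 5 days, at least 5 of 9 placements are missed under every convention tried, and all 9 under some. For longer episodes the shortfall shrinks and, with some conventions, disappears. The threshold mismatch between note [1] and Listing 39 does not depend on what a visit means.

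The conclusion assumes study-day visits and that display 3.16 is meant to reflect 5.4.4; neither is stated. The effect is confined to display 3.16 and Listing 39. SAP 2.1 makes all analyses descriptive, and no dosing, halting or efficacy conclusion is shown to depend on either display. The correction is still worth making, because it costs little and removes a possible contradiction on the trial's named excipient risk.

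**What to change.** - Derive the flag in display 3.16 and Listing 39 on successive creatinine readings at distinct collection times, in time order, including unscheduled readings.
- Evaluate it within one laboratory source, local or central, and name the source. Creatinine is tested both locally and centrally, and protocol 7.4.6 asks for the central sample at the same time as a local one. Pooling the two would let one paired draw count as two successive readings.
- Reconcile the threshold wording across protocol 5.4.4, note [1] and Listing 39. Which inequality is clinically right is for the sponsor to settle, not this review.
- Show the flag beside discontinuations of investigational product for the renal criterion.
- If the IDMC charter's halting criterion is visit-based, cite it, define visit for twice-daily draws, and report subjects meeting 5.4.4 separately.

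The cost is SAP wording and minor programming. No new data are needed: the readings are already collected, and SAP 11.5.3 already provides for actual times in the listings.
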